#### • True Negative:

 A participant with a negative Cu-SAR-bisPSMA PET/CT (i.e., no unequivocal PET-positive lesion or only equivocal lesion(s) detected) and negative Reference Standard.

## • False Positive:

• A participant who does not meet the TP criteria and has at least one unequivocal Cu-SAR-bisPSMA PET-positive lesion and has an evaluable Reference Standard.

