7.5.2 Assessment of Reference Standard against the ⁶⁴Cu-SAR-bisPSMA PET/CT Results

For the assessment of the Reference Standard against the ⁶⁴Cu-SAR-bisPSMA PET/CT, region-level matching will be used for histopathology, subregion-level matching for imaging and participant-level matching for PSA response to radiation or other salvage focal therapy (refer to Section 7.5.1). Matching of the Reference Standard against the ⁶⁴Cu-SAR-bisPSMA PET/CT results will be completed via statistical programming.

Assessment of **region-level** Reference Standard against the ⁶⁴Cu-SAR-bisPSMA PET/CT results:

- Histopathology: A region that is ⁶⁴Cu-SAR-bisPSMA PET-positive (i.e., includes at least one unequivocal PET-positive lesion) and Reference Standard positive, will be assigned as true positive (TP) for the region-level status.
- Imaging: A subregion that is ⁶⁴Cu-SAR-bisPSMA PET-positive (i.e., includes at least one unequivocal PET-positive lesion) and Reference Standard positive (i.e., includes at least one unequivocal lesion detected on conventional imaging in that subregion), will be assigned as TP. A region that includes at least one TP subregion will be assigned as TP for the region-level status.
- A region that is ⁶⁴Cu-SAR-bisPSMA PET-positive (i.e., includes at least one unequivocal PET-positive lesion) and is Reference Standard negative based on at least 1 evaluable timepoint, will be assigned as false positive (FP) for the region-level status.
- A region that is ⁶⁴Cu-SAR-bisPSMA PET-negative (i.e., no unequivocal PET-positive lesion or only equivocal lesion(s) detected within the subregions) and Reference Standard negative, will be assigned as true negative (TN) for the region-level status.
- A region that has either non-evaluable ⁶⁴Cu-SAR-bisPSMA result for a specific timepoint or has a non-evaluable or inconclusive Reference Standard will not be assigned for that timepoint.

Assessment of **participant-level** Reference Standard against the ⁶⁴Cu-SAR-bisPSMA PET/CT results:

- A participant with at least one TP region AND/OR at least one unequivocal ⁶⁴Cu-SARbisPSMA PET-positive lesion and confirmed PSA response to radiation or other salvage focal therapy, will be assigned as TP for the participant-level status.
- A participant with at least one unequivocal ⁶⁴Cu-SAR-bisPSMA PET-positive lesion who does not meet the above criteria to be deemed TP, will be assigned as FP for the participant-level status.

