10.4.5.1 Primary Efficacy Analyses

The co-primary efficacy endpoints include the following:

- Participant-level CDR on Day 0 scan;
- Participant-level CDR on Day 1 scan;
- Region-level PPV on Day 0 scan;
- Region-level PPV on Day 1 scan.

CDR on a participant-level for each central reader is defined as the proportion of TP participants out of all scanned participants who had at least 1 evaluable reference standard datapoint (as without any follow-up reference data it is not possible to determine if the participant is TP or not, which may bias the results) and will be calculated as follows: CDR = TP/(all scanned participants with at least 1 evaluable reference datapoints).

Participants without a ⁶⁴Cu-SAR-bisPSMA PET/CT scan at a specific timepoint (Day 0 or Day 1) will be excluded from the participant-level CDR calculation for that timepoint. Participants with non-evaluable participant-level Reference Standard results will be excluded from the CDR calculation.

PPV on a region-level for each central reader is defined as the proportion of TP regions out of all positive regions on the ⁶⁴Cu-SAR-bisPSMA PET/CT scan with corresponding evaluable composite Reference Standard data and will be calculated as follows: PPV = TP/(TP+FP).

Regions that are not positive on the ⁶⁴Cu-SAR-bisPSMA PET/CT scan at a specific timepoint (Day 0 or Day 1) will be excluded for the region-level PPV calculation for that timepoint.

Region	Description of Anatomic Region
1	Prostatic
2	Pelvic lymph nodes
3	Extra pelvic lymph nodes
4	Visceral/soft tissue
5	Bone

The anatomic regions for lesions include the following:

The point estimates of CDR and PPV on Day 0 and on Day 1 will be computed along with the 2-sided 95% exact binomial CIs using the Clopper-Pearson method. The primary efficacy analyses will be performed for each central reader.

The following sensitivity analyses of the participant-level CDR and region-level PPV will be performed:

- •
- Based on all participants in the FAS regardless whether there are reference datapoints collected. Missing data will be handled as follows:
 - Worst-case imputation:
 - For the participant-level CDR on Day 0 and on Day 1 based on FAS, participants with missing/non-evaluable composite Reference Standard data will be imputed as non-true positive and included in the denominator.

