## • Non-evaluable:

o A region that has either non-evaluable (NE) Cu-SAR-bisPSMA PET/CT results for a specific timepoint (Day 0 or Day 1) or has a non-evaluable or inconclusive Reference Standard will not be assigned for that timepoint.

Assessments of **Participant-Level** Reference Standard against the Cu-SAR-bisPSMA PET/CT results:

• True Positive:

September 4, 2024 CONFIDENTIAL Page 22 of 46

- A participant with at least one TP region and/or at least one unequivocal Cu-SAR-bisPSMA positive lesion in any region and a confirmed PSA response to radiation or other salvage focal therapy.
  - Confirmed PSA response following radiation or other salvage focal therapy (as long as no concomitant ADT is given) = total PSA decline ≥50% from baseline, confirmed by a 2nd value within 4 weeks per Prostate Cancer Working Group 3 criteria.

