#### • Non-evaluable:

 A participant that has either non-evaluable Cu-SAR-bisPSMA PET/CT results for a specific timepoint (Day 0 or Day 1) or has a non-evaluable or inconclusive Reference Standard will not be assigned for that timepoint.

False negative results (region or participant-level) will not be assigned as there is no way to determine whether the disease was initially present, or whether the disease has developed since the acquisition of the baseline and Cu-SAR-bisPSMA imaging. For summarization purposes only, these will be considered "Test Negative" defined as a negative Cu-SAR-bisPSMA PET/CT result within region-level or participant-level and a positive Reference Standard within region-level or participant-level.

Full programmatic details of the algorithm listed above to define Cu-SAR-bisPSMA scan status, reference panel status, and the assessment comparing the two at the subregion-level, region-level, and participant-level will be given in a supplemental analysis document labelled: CLP06\_Primary\_Analysis\_Supplement.xlsx.

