#### 9.14.1 Primary Efficacy Analyses

The co-primary efficacy endpoints are the following:

- Participant-level CDR at Day 0.
- Participant-level CDR at Day 1.
- Region-level PPV at Day 0.
- Region-level PPV at Day 1.

September 4, 2024 CONFIDENTIAL Page 28 of 46

 $\underline{CDR}$  on a participant-level for each central reader is defined as the proportion of TP participants out of all scanned participants who had at least 1 evaluable reference standard datapoint collected and is calculated as:  $\overline{CDR} = \overline{TP}/(all\ scanned\ participants\ with at least 1 evaluable reference datapoint) x 100.$ 

Participants without a Cu-SAR-bisPSMA PET/CT scan at the specific timepoint (Day 0 or Day 1) will be excluded from the participant-level CDR calculation for that timepoint. Participants with non-evaluable participant-level Reference Standard results will be excluded from the CDR calculation

PPV is measured on a region-level (the primary endpoint will be calculated including all 5 regions as a whole) for each central reader and is defined as the proportion of TP regions out of all positive regions on the  $^{64}$ Cu-SAR-bisPSMA PET/CT scan with corresponding evaluable composite Reference Standard data and will be calculated as: PPV = TP/(TP + FP) x 100, where FP = False Positive.

Regions that are not positive on the Cu-SAR-bisPSMA PET/CT scan at a specific timepoint will be excluded from the region-level PPV for that timepoint. PET/CT positive regions without corresponding evaluable composite Reference Standard results will also be excluded.

The anatomic regions for the PPV calculation are the following:

- Region 1 = Prostatic
- Region 2 = Pelvic lymph nodes
- Region 3 = Extra pelvic lymph nodes
- Region 4 = Visceral/soft tissue
  - o This region is incorrectly labeled as Region 5 in the raw data and will be recoded
- Region 5 = Bone
  - o This region is incorrectly labeled as Region 4 in the raw data and will be recoded

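### Participant-level false positive is not tied to the PET-positive region, so an unverified finding can be scored as an error in the secondary participant-level PPV, FPR and TNR

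*SAP*

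**What the plan says.** **Participant level.** The SAP (7.8, False Positive) scores as FP "A participant who does not meet the TP criteria and has at least one unequivocal" PET-positive lesion, provided that he also meets the condition "and has an evaluable Reference Standard". Protocol 7.5.2 is a plain default: a PET-positive participant "who does not meet the above criteria to be deemed TP, will be assigned as FP for the participant-level status". Both documents then leave unassigned a participant who has a non-evaluable PET result "or has a non-evaluable or inconclusive Reference Standard will not be assigned for that timepoint". A participant is TP if he has at least one TP region, or a PET-positive lesion in any region together with a confirmed PSA response to radiation or other salvage focal therapy.

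**Region level.** A region whose reference is non-evaluable or inconclusive is not assigned (Protocol 7.5.2, SAP 7.8). SAP 9.14.1 excludes PET-positive regions without a corresponding evaluable reference from region-level PPV.

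**CDR.** The denominator is set separately. SAP 9.14.1 counts TP participants "out of all scanned participants who had at least 1 evaluable reference standard datapoint collected" and excludes men whose participant-level Reference Standard is non-evaluable. Protocol 10.4.5.1 gives the reason for requiring reference data: "as without any follow-up reference data it is not possible to determine if the participant is TP or not, which may bias the results".

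**Who decides evaluability.** The expert panel records non-evaluable or inconclusive when it judges the information insufficient (Protocol 7.5.1). It works without knowledge of the PET result (Protocol 3.1 and 4.3). The full algorithm is left to a separate supplement (SAP 7.8).

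**The concern.** Take a man who is PET-positive in bone only. The bone reference is inconclusive, the pelvis has been assessed and is negative, and he has no confirmed PSA response. His bone region is unassigned and leaves region-level PPV. If the panel calls his overall Reference Standard evaluable, he is FP at participant level, although the finding that makes him PET-positive was never tested.

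Participant-level PPV, participant-level FPR and the SAP's participant-level TNR = TN/(TN + FP) (SAP 9.14.2) would then count an unverified finding as an error. He would also enter the FP subgroups for PSA (9.14.3.6) and biodistribution (9.16). The region-level and participant-level results would rest on different standards of verification.

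**Working it through.** **1. The plan's own figures.** Protocol 10.3 and SAP 4.2 assume 40 evaluable participants, CDR 42%, 65% PET-positive and 1.3 positive regions per positive participant.
- CDR: the smallest count out of 40 whose exact 95% lower limit exceeds 20% is 14 (14/40 gives 20.6%; 13/40 gives 18.6%). P(X ≥ 14 | n = 40, p = 0.42) = 85.5%, as stated (more than 85%).
- Enrolment: 40/0.80 = 50, as stated.
- Positive regions: 40 × 0.65 × 1.3 = 33.8, about 34, as stated. With 34 regions at least 20 TP are needed (lower limit 40.7%), and power at 65% is 82.6%, as stated (more than 80%).

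The point does not dispute these figures. They supply the planning case below.

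**2. Does anything in the plan close the gap?**
- The panel is blinded to PET, so it cannot ask whether the PET-positive region was verified.
- Matching is done by statistical programming (Protocol 7.5.2), so the written rule decides.
- The Per Protocol set (SAP 6.0) asks for an evaluable participant-level assessment and at least one evaluable region. That can be a different region.
- For CDR, worst-case imputation reaches participants with missing, non-evaluable or inconclusive reference data, and the tipping-point analysis those with missing or non-evaluable data (SAP 9.14.1.1). A man classed as evaluable is reached by neither.
- The non-evaluable rule helps only if his participant-level Reference Standard is itself called non-evaluable or inconclusive. The documents do not say when that follows from one unverified region.

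**3. Size for the secondary endpoints.** PET-positive: 40 × 0.65 = 26. TP: 40 × 0.42 = 16.8, taken as 17. PET-positive non-TP: 26 − 17 = 9. PET-negative: 40 − 26 = 14. Let k of the 9 have no evaluable reference in any PET-positive region; k is an assumption.
- PPV as written = 17/26; with the k men unassigned = 17/(26 − k).
- FPR as written = 9/26; unassigned = (9 − k)/(26 − k).
- TNR as written = 14/(14 + 9); unassigned = 14/(14 + 9 − k). This further assumes that all 14 PET-negative men are TN, which the documents do not state.

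| k | PPV | FPR | TNR (if 14 TN) |
|---|---|---|---|
| as written | 65.4% | 34.6% | 60.9% |
| 1 | 68.0% | 32.0% | 63.6% |
| 2 | 70.8% | 29.2% | 66.7% |
| 3 | 73.9% | 26.1% | 70.0% |
| 4 | 77.3% | 22.7% | 73.7% |

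**4. CDR.** FP does not appear in the CDR formula. If the k men are kept in the denominator, CDR is 17/40 = 42.5%. Excluding them gives 17/(40 − k) = 43.6%, 44.7%, 45.9% and 47.2% for k = 1 to 4, always higher. Keeping them and imputing all as TP (p = 1 in a tipping-point analysis) gives (17 + k)/40 = 45.0%, 47.5%, 50.0% and 52.5%.

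**The case against.** **The case may be rare.** Follow-up imaging is required for everyone whatever the PET result, and should include anatomical and molecular imaging (Protocol 7.3.3). One scan can cover several regions, and Protocol 7.5.1 deems regions without positive evidence negative. This stands: no frequency is documented and k is only an assumption. But both documents provide for non-evaluable and inconclusive regions, so the class exists.

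**A reader might infer that one evaluable datapoint in any other region always makes such a man FP.** The documents do not say so. Participant-level evaluability is a panel judgement without a stated rule. He may be called non-evaluable or inconclusive and left unassigned, and a confirmed PSA response makes him TP with no regional reference at all. The supported wording is that he can be scored FP.

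**A reader might infer that the FP rule corrupts the co-primary CDR and that these men should be dropped from it.** His non-TP status in CDR comes from the CDR denominator, not from the FP definition, and PET-negative men are non-TP there too. The Protocol's reason for exclusion speaks of having no follow-up reference data at all; requiring one evaluable datapoint is a stated choice. Dropping only PET-positive, unverified men would make the denominator depend on the scan under test and could only raise CDR. It could turn a miss into a success against the 20% planning bound: 13/40 has a lower limit of 18.6%, but 13/37 has 20.2%.

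**A reader might also want every PET-positive region to be proven negative before FP is assigned.** That would release a man with one region already shown to be FP because a second region was unverified. Nothing in the plan supports that.

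**Conclusion.** The point holds for the secondary participant-level measures. As written, FP does not require evidence in the region that made the man PET-positive, while the plan's own region-level rule does. Scoring such men FP gives each a zero chance of being TP, so PPV can only be too low, FPR too high and the SAP's TNR too low.

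At the planning values, and for an assumed 1 to 4 affected men among 26 PET-positive, participant-level PPV is 65.4% as written against 68.0% to 77.3% if they are unassigned, a gap of 2.6 to 11.9 points. The figures rest on 40 evaluable men, 17 TP and an undocumented k; if k is 0 there is no effect. The Protocol's own TNR, TN over PET-negative participants (the SAP's ANPV), does not use FP and is unaffected.

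No formal hypothesis test is planned (SAP 4.1), and the primary CDR definition can stand. This should be fixed; it is not a fatal flaw.

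**What to change.** In SAP 7.8 and Protocol 7.5.2:
- State that participant-level FP requires at least one PET-positive region to be Reference Standard negative on evaluable evidence.
- State that a PET-positive, non-TP participant with no evaluable reference in any PET-positive region is not assigned at that timepoint for participant-level PPV, FPR and TNR.
- Align the FPR denominator in SAP 9.14.2, which now counts all PET-positive participants with an evaluable reference. The man then leaves both numerator and denominator, and PPV and FPR still add to 100%.
- Carry the same rule into the programming supplement.

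Keep the primary CDR denominator of Protocol 10.4.5.1 and SAP 9.14.1. Extend the tipping-point analysis in SAP 9.14.1.1 to these men, so that CDR is shown with them counted as non-TP (p = 0) through to TP (p = 1), and report how many there are by reader and timepoint.

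The cost is a few sentences and some programming. The secondary endpoints lose a few participants and so a little precision.

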#### • Non-evaluable:

 A participant that has either non-evaluable Cu-SAR-bisPSMA PET/CT results for a specific timepoint (Day 0 or Day 1) or has a non-evaluable or inconclusive Reference Standard will not be assigned for that timepoint.

False negative results (region or participant-level) will not be assigned as there is no way to determine whether the disease was initially present, or whether the disease has developed since the acquisition of the baseline and Cu-SAR-bisPSMA imaging. For summarization purposes only, these will be considered "Test Negative" defined as a negative Cu-SAR-bisPSMA PET/CT result within region-level or participant-level and a positive Reference Standard within region-level or participant-level.

Full programmatic details of the algorithm listed above to define Cu-SAR-bisPSMA scan status, reference panel status, and the assessment comparing the two at the subregion-level, region-level, and participant-level will be given in a supplemental analysis document labelled: CLP06\_Primary\_Analysis\_Supplement.xlsx.

## 7.9 Analysis Visit Windows for Reference Datapoints

A reference datapoint defined in the previous sections can occur at anytime post-Day 1 on study. There are 2 reference timepoints of interest in the analysis, Day 90 and Day 180. These timepoints (visit labels) are the occasions at which information was collected on clinical events that occurred between the previous visit/reference timepoint and the current visit/reference timepoint i.e., the visit/reference timepoint represents events that occurred over a window of time up to that

September 4, 2024 CONFIDENTIAL Page 23 of 46

Protocol: CLP06 Statistical Analysis Plan, Version 1.0

visit/reference timepoint and does not represent only events which occurred at the specific timepoint/day. The following describes the analysis windows surrounding these analysis visits:

- 1. The visit described in the visit form completed for the assessment will be used as the analysis visit.
- 2. If the visit is considered unscheduled or out of the protocol defined visit windows (Day 75-105 for Day 90 and 165-195 for Day 180), then the following analysis visit windows are used:
  - a. Day 90 Analysis Visit: Day 2 Day 120 (or first analysis visit post-baseline)
  - b. Day 180 Analysis Visit (only if a Day 90 already exists): Day 121 End of Study.

#### 8.0 DEVIATIONS FROM PROTOCOL ANALYSES

**Table 3** Deviations from Protocol Analyses

Analysis Endpoint and SAP Section	Protocol v3.0 Original Analysis	Updated Analysis	Rationale
Exploratory Outcome: Function of Baseline	This analysis includes Lesion-to-background ratio as per protocol.	Lesion-to-background ratio not included in this exploratory analysis.	Inclusion of lesion-to- background ratio is not deemed necessary or
Variables Section 9.14.3.2.			informative in this analysis.

#### 9.0 STATISTICAL ANALYSES

#### 9.1 Screened Participants

Using the All Participants Analysis set, the number of screened patients will be summarized as well as the number and percentage of patients who were enrolled and reasons for non-enrollment. Inclusion/exclusion findings will also be listed.

## 9.2 Patient Disposition

Patient disposition will be summarized for the Enrolled Analysis Set. Summaries will include:

Number of patients who completed the study.

September 4, 2024 CONFIDENTIAL Page 24 of 46

Number of patients who discontinued from the study and reason for discontinuation.
 Patient disposition data will also be presented in listings.

## 9.3 Analysis Sets

Using the Enrolled analysis set, the number and percent of patients in the Safety, FAS, PP, and Biodistribution analysis sets will be provided. Reasons for exclusion from the FAS, PP and Biodistribution analysis sets will be summarized and presented in listings.

#### 9.4 Protocol Deviations

In accordance with International Council for Harmonisation (ICH) E3, Sponsor-defined eligibility violations and important (major) protocol deviations will be identified and listed. Deviations that exclude a participant from the PP Population will also be identified. Protocol deviations will also be tabulated by type of deviation and major deviations will be summarized separately by type of deviation in the Enrolled Analysis Set.

## 9.5 Demographics and Baseline Characteristics

Demographic and baseline characteristics will be listed and summarized descriptively for the Safety Analysis Set, FAS, and PP Analysis Set. The following demographic and baseline data will be summarized: sex, age, race, ethnicity, height, weight, BMI, and Eastern Cooperative Oncology Group (ECOG) status. Age is calculated in the Electronic Data Capture (EDC) from date of birth to date of informed consent.

A demographic listing will also be provided.

## 9.6 Medical and Surgical History

Medical and Surgical history collected at screening will be coded using Medical Dictionary for Regulatory Activities (MedDRA), version 25. Medical and Surgical history will be summarized for the Safety Analysis Set by system organ class and preferred name.

Medical and Surgical history will be listed.

## 9.7 Prostate Cancer Related History

Relevant medical history related to PC will be summarized for the Safety Analysis Set, including initial prostate cancer diagnosis (PC pathology results), location of metastasis (only locations that at least 1 participant had are included), initial diagnosis stage per American Joint Committee on Cancer (AJCC) classification, initial diagnosis staging (T, N and M), initial Gleason score, time

September 4, 2024 CONFIDENTIAL Page 25 of 46

from initial diagnosis to Day 0, time from biochemical recurrence to Day 0, and PSA levels at biochemical recurrence.

All relevant PC related history will also be listed.

#### 9.8 Prior and Concomitant Medications

Verbatim terms on case report forms will be mapped to Anatomical/Therapeutic/Chemical (ATC) class and generic drug name using the World Health Organization (WHO) drug dictionary, WHO Drug – Global B3, March 2022.

Prior medications are those medications started before the administration of Cu-SAR-bisPSMA. Concomitant medications are those medications taken after the administration of Cu-SAR-bisPSMA. As such, prior medications continued after the use of study drug are also considered concomitant medications. Prior and concomitant medications will be summarized for the Safety Analysis Set by ATC class (level 3) and preferred name. Patients receiving the same medication more than once are counted only once for each ATC class and preferred name.

All medications with partial or missing dates and times recorded on the concomitant medication eCRF will be considered concomitant unless a partial stop date and time clearly indicates it was stopped before the administration of Cu-SAR-bisPSMA.

Prior and concomitant medications will be listed by patient.

